| 6. | Following responses from the "Since Last Visit" version of the C-SSRS 7-day follow-up visit of double-blind pahse 3 trial, (ie, Trial 405-201-00013 or Trial 405-201-00014): Subjects with a response of "Yes" on the C-SSRS Suicidal Ideation Item 4 (Active Suicidal Ideation with Some Intent to Act, Without Specific Plan) at entry, OR Subjects with a response of "Yes" on the C-SSRS Suicidal Ideation Item 5 (Active Suicidal Ideation with Specific Plan and Intent) at entry, OR Subjects with a response of "Yes" on any of the 5 C-SSRS Suicidal Behavior Items (actual attempt, interrupted attempt, aborted attempt, preparatory acts, or behavior) at entry, |
| | OR Subjects who, in the opinion of the investigator (including consideration of responses on the C-SSRS throughout Trial 405-201-00013 or Trial 405-201-00014), present a serious risk of suicide. Note: "Entry" is defined as the 7-day follow-up of Trial 405-201-00013 or Trial 405-201-00014. |
| 7. | Subjects with newly developed psychiatric or medical condition that would be exclusionary under the criteria listed for Trial 405-201-00013 or Trial 405-201-00014. |
| 8. | Subjects that have a positive alcohol test (via breathalyzer or blood), a positive drug screen for cocaine, or other illicit drugs (excluding marijuana). Subjects with a positive drug screen for confirmed prescription medications at baseline will not be permitted to continue participation in Trial 405-201-00015. NOTE: Subjects that test positive for marijuana may be permitted to be enrolled if they have no evidence of a substance use disorder, and if they agree to refrain from use for the duration of the trial. Allowance for subjects testing positive for marijuana at screening require explicit approval from the medical monitor. |
| 9. | Any new or developing safety concerns related to vital signs in the opinion of the investigator during the baseline visit. |

Confidential - Proprietary Information

| Tabl | e 3.4.3.1-1 Exclusion Criteria for Rollover Subjects from |
|-------|---|
| | Trial 405-201-00013 or Trial 405-201-00014 |
| 10. | The following laboratory test and ECG results are exclusionary: |
| | 1) Platelets \leq 75,000/mm ³ |
| | 2) Hemoglobin $\leq 9 \text{ g/dL}$ |
| | 3) Neutrophils, absolute $\leq 1000/\text{mm}^3$ |
| | 4) AST > $2 \times$ upper limit of normal |
| | 5) ALT > 2 × upper limit of normal |
| | 6) Creatinine $\geq 2 \text{ mg/dL}$ |
| | 7) HbA ₁ c \geq 7% |

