- A urine pregnancy test will be performed for all FOCBP. If the urine pregnancy test is positive, the result should be confirmed with a serum pregnancy test. Subjects with a positive serum test result will be excluded from the trial.
- Urine will be collected from all potential subjects for urinalysis and urine screen(s) for drugs of abuse. See Table 3.4.3.2-1 for exclusions based on outcome of urine drug screen(s).
- If subjects are taking disallowed medications and they are able to taper appropriately and safely, they will do so during the screening period. If medication taken is for ADHD, a minimum of 1 week off stimulants and 3 weeks off nonstimulants will be required before baseline. A complete washout schedule, including common excluded medications and herbal preparations, is provided in Section 4.1.
- AE recording will begin with the signing of the eICF for Trial 405-201-00015.

The sponsor reserves the right to utilize external quality oversight methods to ensure the validity of diagnosis, severity of illness, and other factors determining appropriateness of subject selection.

3.7.1.1.2.2 Baseline

If the subject is found to be eligible for the trial during the screening, the subject will attend a baseline visit (Visit 2) during which the following procedures will be completed prior to the subject starting open-label IMP:

- Inclusion/exclusion criteria will be verified. Review of inclusion/exclusion criteria at the baseline visit will be based on assessments performed during screening.
- Medications taken during the screening period will be reviewed and documented.
- A qualified rater will administer the AISRS.
- A qualified rater will administer the CGI-S.
- The investigator (or qualified designee) will complete the "Since Last Visit" C-SSRS form.
- Subjects will complete the AIM-A.
- CCI
- A physical examination will be performed.

Confidential - Proprietary Information

52

- Vital sign measurements will be recorded.
- A standard 12-lead ECG will be performed after the subject has been supine and at rest for at least 5 minutes. The ECG is to be completed before any blood is drawn.
- Blood samples will be collected for clinical laboratory tests (hematology and serum chemistry [including HbA₁c, TSH, and PT/INR]) after a minimum 8-hour fast. Vital sign and ECG assessments should be completed before any blood samples are collected.
- Alcohol testing will be conducted via a blood test or using a breathalyzer.

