3.7.4.6.2 Suicidality

Suicidality will be monitored during the trial (Table 3.7-1 and Table 3.7-2 for rollover subjects and Table 3.7-3 and Table 3.7-4 for de novo subjects) using the C-SSRS.³⁹ The C-SSRS is a semi-structured interview that captures the occurrence, severity, and frequency of suicide-related thoughts and behaviors during the assessment period.³⁹ The interview includes definitions and suggested questions to solicit the type of information needed to determine if a suicide-related thought or behavior has occurred. The interview and rating for the C-SSRS must be completed by a licensed clinician who has been successfully trained to rate this scale by the sponsor or a designee, and is medically responsible for the subject. Documentation of trial training should be maintained in the investigational site's files.

This trial will use the "Baseline/Screening" and "Since Last Visit" versions of the scale. The "Baseline/Screening" version, which assesses the life-time experience of the subject with suicide events and suicidal ideation and the occurrence of suicide events or ideation

Confidential - Proprietary Information

66

within a specified time period prior to entry into the trial, will be completed for all de novo subjects at the screening visit to determine the eligibility. Any subject with active suicidal ideation within the last 30 days, suicidal behaviors within the last year, or who in the clinical judgment of the investigator presents a serious risk of suicide should be excluded from the trial (see Table 3.4.3.1-1 for rollover subjects and Table 3.4.3.2-1 for de novo subjects). The "Since Last Visit" C-SSRS form will be completed at all other in-clinic visits for all subjects (rollover and de novo).

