#### 9.5 Suicidality Data

Suicidality will be monitored during the study using the C-SSRS and will be summarized as number and percentage of subjects reporting any suicidal behavior, ideation, behavior by type (4 types), ideation by type (5 types) and treatment emergent suicidal behavior and ideation. Summary will be provided for the open-label treatment period for the Safety Sample.

Suicidality is defined as report of at least one occurrence of any type of suicidal ideation or at least one occurrence of any type of suicidal behavior during assessment period (count each person only once).

Treatment emergent suicidal behavior and ideation is summarized by four types: Emergence of suicidal ideation, Emergence of serious suicidal ideation, Worsening of suicidal ideation, Emergence of suicidal behavior.

Emergence of suicidal behavior/ideation is defined as report of any type of suicidal behavior/ideation during treatment when there was no baseline suicidal behavior/ideation.

Emergence of serious suicidal ideation is defined as observation of suicidal ideation severity rating of 4 or 5 during treatment when there was no baseline suicidal ideation.

Worsening of suicidal ideation is defined as a suicidal ideation severity rating that is more severe than it was at baseline.

For the open-label treatment period analyses, the last available measurement prior to the first dose of open-label IMP is being used as "Baseline".

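### The C-SSRS baseline in SAP 9.5 is, as scheduled, a short-window form, so earlier ideation that is absent in that window and recurs on treatment is counted as emergent

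*SAP*

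**What the plan says.** SAP 9.5 defines the C-SSRS baseline for the open-label analyses: "the last available measurement prior to the first dose of open-label IMP is being used as 'Baseline". This is the general baseline rule of SAP 7.1, with no distinction between versions of the form.

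Three definitions in SAP 9.5 build on it:
- Emergence of ideation or behavior is "report of any type of suicidal behavior/ideation during treatment when there was no baseline suicidal behavior/ideation".
- Emergence of serious ideation is a "suicidal ideation severity rating of 4 or 5 during treatment when there was no baseline suicidal ideation".
- For worsening: "Worsening of suicidal ideation is defined as a suicidal ideation severity rating that is more severe than it was at baseline".

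Which form comes last before dosing follows from the protocol:
- **De novo.** The Baseline/Screening version, which asks about lifetime and recent history, is completed at screening (Protocol 3.7.1.1.2.1). At the baseline visit, "The investigator (or qualified designee) will complete the 'Since Last Visit' C-SSRS" form (Protocol 3.7.1.1.2.2).
- **Rollover.** The C-SSRS from the parent trial's 7-day follow-up may serve as baseline (Protocol 3.7.1.1.1). Exclusion 6 of Table 3.4.3.1-1 identifies its version: "Following responses from the 'Since Last Visit' version of the C-SSRS 7-day follow-up visit".
- **All other in-clinic visits.** Protocol 3.7.4.6.2 and SAP 10.2.5 specify the Since Last Visit version for both cohorts.

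Late rollovers are analysed as de novo subjects (SAP 6) and have C-SSRS at both screening and baseline visits (COVID-19 addendum, Table 1.2-1).

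**The concern.** A Since Last Visit form records only what has happened since the previous C-SSRS. Used alone as baseline, it can show no ideation in a subject whose history includes some. If that ideation returns during treatment, the SAP counts it as emergent, although it may be the subject's usual pattern. Emergence of behavior, serious emergence and worsening all use the same baseline.

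The trial has a single arm and safety is its objective. No control group shows how often such recurrences occur without the drug, so a reader leans heavily on the emergent label in CT-6.4 to CT-6.8. SAP 9 reports rollover and de novo groups side by side. Because their look-backs differ, part of any difference between them could come from the forms alone.

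**Working it through.** The plan gives no figure here, so there is none to reproduce. The check has three parts.

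**1. Length of the baseline window**
- Rollover: about 7 days, from the Week 6 visit to the 7-day follow-up. The parent-trial C-SSRS schedule is not in the documents. If a form fell in between, the window is shorter.
- De novo: at most 28 days, the longest interval allowed between consent and the baseline visit (Protocol 3.1).
- On treatment: reports accumulate over up to 12 in-clinic forms (Weeks 1, 2, 4, 8, 12, 16, 20, 26, 32, 38, 44 and 52).
- Planned mix (SAP 4): 560 rollover and 145 de novo, so 560/705 = 79% have the shorter window.
- If a Day -1 form is missing, the last available form is the screening form. The same column then mixes long and short look-backs.

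**2. Who can enter with a history**
- Rollover (Table 3.4.3.1-1, exclusion 6): excluded for items 4 or 5 or any behavior at entry, or a judged serious risk, "including consideration of responses on the C-SSRS throughout Trial 405-201-00013 or Trial 405-201-00014".
- De novo (Table 3.4.3.2-1, exclusion 7): excluded for items 4 or 5 in the last 6 months or behavior in the last 2 years.
- Protocol 3.7.4.6.2 and SAP 10.2.5: active ideation within 30 days or behavior within a year is excluded. The protocol text refers to both tables but does not match them.

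These passages conflict and must be reconciled. Under any of them, older or milder ideation can enter.

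**3. Illustration**

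Assumptions: a subject with recurrent ideation, no drug effect, episodes arising at random at a constant rate with mean interval p, and every episode reported. With look-back b and time on treatment T, in days, the subject is labelled emergent if no episode falls in the look-back and at least one falls on treatment:

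P = exp(−b/p) × (1 − exp(−T/p))

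The 6-month look-back is taken as 182 days, the period that the de novo table applies to items 4 and 5. For p = 182:
- b = 7, T = 182: 0.962 × 0.632 = 61%
- b = 182, T = 182: 0.368 × 0.632 = 23%
- b = 7, T = 364: 0.962 × 0.865 = 83%
- b = 182, T = 364: 0.368 × 0.865 = 32%

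| Mean interval p | T | b = 7 | b = 28 | b = 182 |
|---|---|---|---|---|
| 182 days | 26 weeks | 61% | 54% | 23% |
| 182 days | 52 weeks | 83% | 74% | 32% |
| 56 days | 26 weeks | 85% | 58% | 4% |
| 56 days | 52 weeks | 88% | 61% | 4% |

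The 26-week rows deserve more weight. Of about 720 subjects, the protocol expects about 300 to reach 6 months and about 100 to reach 52 weeks (Synopsis; section 3.3.1).

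The effect of the look-back does not depend on T. At p = 182, moving from 182 days to 7 multiplies the chance by exp(175/182) = 2.6. Between the cohorts (28 days against 7), the factor is exp(21/182) = 1.12 at p = 182 and exp(21/56) = 1.45 at p = 56. The direction is the same for any positive recurrence rate.

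**The case against.** There is a good case for leaving SAP 9.5 alone. Last value before dosing is the trial's general baseline. Treatment-emergent is a label about timing, and SAP 9.5 makes no causal claim. The C-SSRS is an additional safety variable summarised descriptively (Protocol 3.5.4 and 7.6.6). CT-6.1 to CT-6.3 count ideation and behavior without reference to baseline, and listings CT-6.5 to CT-6.8 allow case review. Any error is toward over-reporting. De novo criteria also exclude a current major depressive episode, bipolar and psychotic disorders, posttraumatic stress disorder and clinically significant borderline personality disorder, which shrinks the pool.

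Most of this stands, and it supports keeping the current definition as the main one. It does not remove the point: over-labelling can hide true new onset among recurrences, and the planned tables do not separate the two.

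The objection to replacing the definition outright also stands. With a worst-of-all-forms baseline, a subject with mild ideation months earlier who reaches 4 or 5 on treatment would leave the serious-emergence row, because SAP 9.5 requires no baseline ideation of any kind. If parent-trial double-blind forms were used for some arms only, look-back would depend on parent treatment.

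A reader might infer that most cases labelled emergent will be recurrences, or that the entry rules do nothing. The documents support neither. They give no prevalence of prior ideation and no recurrence rate, and the entry rules do remove recent serious cases.

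**Conclusion.** The point holds as a matter of definition. As scheduled, the C-SSRS baseline is a short-window form in both cohorts, the history on the de novo screening form plays no part in it, and recurrence after a negative short-window form is counted as emergence. A recurrence is not misclassified as emergence if ideation also appears on the baseline form.

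The size is unknown. The percentages describe one hypothetical kind of subject under a constant recurrence rate and no drug effect. They are not estimates for this trial, and no expected count follows from them. The one-week rollover window also rests on an unseen parent-trial schedule. It would go too far to say that the tables will show a false drug signal, or that the SAP definition is invalid. What is missing is a way to tell recurrence from new onset, and a statement of the look-back behind each column.

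**What to change.** 1. Keep the SAP 9.5 definition as the main row in CT-6.4.
2. Add a supplementary row with baseline as the worst rating over the pre-dose forms:
   - De novo: the recent-history part of the screening form plus the Day -1 form.
   - Rollover: parent-trial forms from before parent dosing, where available, plus the 7-day form. Apply the same rule to every parent treatment group, so that look-back does not depend on parent arm and ideation arising on centanafadine during double-blind treatment is not absorbed into baseline.
3. In that row, count serious emergence as a rating of 4 or 5 with no pre-dose rating of 4 or 5, so that earlier mild ideation does not remove a serious case.
4. In CT-6.5 to CT-6.8, flag subjects with any recorded prior ideation or behavior.
5. Footnote each cohort's look-back. State what applies when the Day -1 form is missing, and which screening version late rollovers have: addendum Table 3.2-1 refers to a Since Last Visit form dated from their last parent-trial visit.
6. Reconcile the exclusion periods in Protocol 3.7.4.6.2 and SAP 10.2.5 with Tables 3.4.3.1-1 and 3.4.3.2-1.

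The cost is SAP wording and a little extra programming. Rollover subjects keep their subject ID (Protocol 3.3.2), so linkage should be simple, but which parent-trial forms exist must be confirmed. The downside is fewer events labelled emergent, in the supplementary row only.

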## 9.6 SMWQ

Medication withdrawal symptoms assessed by SMWQ total scores at the scheduled visits during the open-label treatment period and follow-up period will be summarized for the Safety Sample by parent study treatment group for rollover subjects, de novo subjects and overall. The number of patients, mean, median, range and standard deviation will be presented.

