3.7.1.3 Follow-up Period

All subjects, whether they complete the trial or are withdrawn prematurely for any reason, will be followed up for a safety evaluation during a 10-day follow up period (follow-up telephone calls at 1, 3, and 5 days after the last dose of IMP, in-clinic visits 2 and 7 days after the last dose of IMP, and a follow-up telephone call [or web, or other acceptable means of contact] 10 days after the last dose of IMP).

The following procedures will be performed at the 1-day, 3-day, and 5-day follow-up visit:

- The SMWQ questionnaire will be completed remotely.
- AEs will be recorded.
- Concomitant medications will be recorded.

The following procedures will be performed at the 2-day and 7-day follow-up visit:

Confidential - Proprietary Information

58

- A qualified rater will administer the AISRS.
- The SMWQ questionnaire will be completed in-clinic.
- Vital sign measurements will be recorded.
- Alcohol testing may be conducted via a blood test or using a breathalyzer.
- Urine will be collected for urine screen(s) for drugs of abuse.
- The investigator (or qualified designee) will complete the "Since Last Visit" C-SSRS form.
- AEs and concomitant medications will be recorded.

The following procedures will be performed at 10-day follow-up contact:

- The SMWQ questionnaire will be completed remotely.
- AEs and concomitant medications will be recorded.

Depending upon the type of follow-up required, other evaluations or tests may be conducted or performed.

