7.6.5 Study Medication Withdrawal Symptoms

Medication withdrawal symptoms for all subjects will be assessed using SMWQ. Summary statistics for SMWQ total scores at the scheduled visit(s) will be provided.

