## 10.2.4 Study Medication Withdrawal Questionnaire (SMWQ)

The SMWQ is a questionnaire to assess withdrawal symptoms. The SMWQ is a modification of the Amphetamine Withdrawal Questionnaire in which the terms "amphetamines and methamphetamine" are replaced with the term "the study medication." The SMWQ is assessed at Week 52/ET in the open-label treatment period and at 1, 2, 3, 5, 7, and 10 days after the last dose of IMP in the follow-up period.

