- CT-12.1.1 Criteria for Potentially Clinically Relevant Abnormalities in ECG Evaluations
- CT-12.2.1 Listing of Potentially Clinically Relevant Abnormalities in ECG Evaluations (Safety Sample)
- CT-12.2.2 Incidence of Potentially Clinically Relevant Changes in ECG Evaluations (Safety Sample)
- CT-12.2.3 Mean Change from Baseline in Electrocardiogram Results (Safety Sample)
- CT-12.3.1 Listing of Categorical Changes in QT/QTc (Safety Sample)
- CT-12.3.2 Incidence of Categorical Changes in QT/QTc (Safety Sample)
- CT-13 Summary of Mean Study Medication Withdrawal Questionnaire (SMWQ) Total Score During the Open-Label Treatment Period and Follow-up Period (Safety Sample)
- CT-14 Summary of Medication Handling Irregularity (Safety Sample)
- CT-15.1 Summary of ESAMs Reported as Abuse Potential AEs by System Organ Class and MedDRA Preferred Term (Safety Sample)
- CT-15.2 Summary of Non-Adverse Events Reported as Findings (ESAM) (Safety Sample)

Confidential - Proprietary Information 29 15 September 2021 Until the information herein is released by Otsuka to the public domain, the contents of this document are Otsuka confidential information and should not be duplicated or re-distributed without prior written consent of Otsuka. 29

CCI		

Confidential - Proprietary Information3015 September 2021Until the information herein is released by Otsuka to the public domain, the contents of this document are Otsuka
confidential information and should not be duplicated or re-distributed without prior written consent of Otsuka.

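### The planned SMWQ summary describes each visit separately and does not estimate each subject's change after the last dose

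*SAP*

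**What the plan says.** SAP 9.6 sets the analysis: "Medication withdrawal symptoms assessed by SMWQ total scores at the scheduled visits during the open-label treatment period and follow-up period will be summarized", in the Safety Sample, by parent-study treatment group for rollover subjects, for de novo subjects and overall. The statistics are "The number of patients, mean, median, range and standard deviation will be presented". Protocol 7.6.5 is no wider: "Summary statistics for SMWQ total scores at the scheduled visit(s) will be provided". The one SMWQ output in SAP Section 12 is CT-13, "Summary of Mean Study Medication Withdrawal Questionnaire (SMWQ) Total Score During the Open-Label Treatment Period and Follow-up Period".

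SAP 10.2.4 gives the schedule: "The SMWQ is assessed at Week 52/ET in the open-label treatment period", then at "1, 2, 3, 5, 7, and 10 days after the last dose of IMP in the follow-up period". Protocol 3.7.1.3 applies the follow-up to completers and early withdrawals alike: "All subjects, whether they complete the trial or are withdrawn prematurely for any reason, will be followed up".

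Three other places matter. SAP Section 9 makes observed cases and last visit the default for safety data. Protocol 3.1 asks for early-termination evaluations promptly but sets no limit relative to the last dose. SAP 10.1 drops evaluations made more than three days after the last open-label dose from the treatment-period analyses, and so keeps those made within three days.

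**The concern.** Withdrawal is a change within a person after the drug stops. The schedule collects what is needed to measure it: one end-of-treatment score and six later scores in the same subjects. The plan then reports seven unlinked rows. A reader of CT-13 would have to subtract one row from another, although the rows may hold different people and the table gives no SD of the change.

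The SMWQ stands out in this respect. SAP Section 12 lists mean-change tables for AISRS, CGI-S, AIM-A, laboratory tests, vital signs and ECG. The general baseline in SAP 7.1 (last value before the first open-label dose) cannot serve here, because no pre-treatment SMWQ is scheduled. The SMWQ needs its own reference, and neither document names one.

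At stake is the reading of a named safety assessment. A modest average rise could look smaller or larger because of who missed a contact, or because the reference score was already off drug.

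**Working it through.** The documents state no SMWQ figure and no precision target, so there is nothing to reproduce. The check has four parts. All values of r, g, the correlation and the SD are assumptions, in units of one SMWQ SD.

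**1. What a difference between rows measures.** Let r be the share of subjects with a Week 52/ET score who also have a score on a given follow-up day. Let g be the Week 52/ET mean of those with the follow-up score minus that of those without. If everyone with a follow-up score also has a reference score, then

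row difference = mean change in those observed + (1 − r) × g.

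| r | size of g (SD) | shift (SD) |
|---|---|---|
| 1.0 | any | 0 |
| 0.9 | 0.5 | 0.1 × 0.5 = 0.05 |
| 0.7 | 0.5 | 0.3 × 0.5 = 0.15 |
| 0.7 | 0.8 | 0.3 × 0.8 = 0.24 |

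The shift also vanishes if g = 0.

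**2. What pairing does and does not cure.** Write d = (1 − r) × g, the shift in reference mean among those retained. Suppose missingness depends only on the Week 52/ET score, SDs are equal and the correlation is rho. Measured against the true mean change in all subjects, the row difference has bias rho × d and the paired change has bias −(1 − rho) × d. At rho = 0.4 these are 0.4d and −0.6d, so pairing is the more biased. At 0.5 they are equal in size. Above 0.5 pairing is the less biased.

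A simulation agrees (1,000,000 subjects, rho = 0.5, 70% retained, higher scorers likelier to be missing, true rise 0.20 SD):

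| dependence of missingness on the reference score | g | row difference | paired change |
|---|---|---|---|
| none | 0 | 0.20 | 0.20 |
| moderate | −0.47 | 0.13 | 0.27 |
| strong | −0.84 | 0.08 | 0.33 |

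By the formula, the moderate case has d = 0.3 × (−0.47) = −0.14. The row difference is then 0.20 − 0.07 = 0.13 and the paired change 0.20 + 0.07 = 0.27. With no true rise, the two selective cases gave row differences of −0.07 and −0.12, and paired changes of 0.07 and 0.13.

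**3. Precision.** The 95% half-width of the paired change is 1.96 × sqrt(2(1 − rho)/n). Treating the two rows as independent gives 1.96 × sqrt(2/n). The sample sizes are illustrative.

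| n | paired, rho = 0.3 | paired, rho = 0.5 | paired, rho = 0.7 | rows treated as independent |
|---|---|---|---|---|
| 300 | 0.134 | 0.113 | 0.088 | 0.160 |
| 100 | 0.232 | 0.196 | 0.152 | 0.277 |

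The paired interval cannot be rebuilt from CT-13, because the SD of the change is not planned.

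**4. The reference score.** Under the three-day rule in SAP 10.1, an early-termination score could be kept as on-treatment although it was taken as late as the Day 1, 2 or 3 follow-up contacts. The readable part of the scale list in SAP 10.1 does not name the SMWQ, so it is unclear whether the rule applies. If it does not, no stated limit on the timing of the reference score remains.

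**The case against.** The strongest reply is that the SMWQ is an additional descriptive safety measure in an open-label trial, and that the SAP does what protocol 7.6.5 asks. All seven scores come from the same subjects and sit in one table. The plan gives n, median, range and SD as well as the mean, so a changing denominator would be visible. Protocol 3.8.3.3 wants early-termination evaluations at the time of withdrawal, which limits late reference scores. Adverse events are collected at all six follow-up contacts and AISRS at Days 2 and 7, so the SMWQ is not the only evidence on withdrawal. All of this stands. It limits the harm but does not supply a paired estimate.

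A reader might infer more than the documents support:

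- **That the trial cannot show whether symptoms rose.** It can. With near-complete follow-up, the row difference equals the mean change. The gap is in the planned analysis, and the documents give no follow-up missing-data rate.
- **That pairing removes the selection caused by missed contacts.** Part 2 of the working shows that it does not. It aligns who is compared, but can overstate a rise where the row difference understates it.
- **That the gain in precision measures the harm.** No SMWQ test or interval is planned for pairing to improve, and the correlation is unknown.
- **That each subject's largest increase, averaged, would be a good summary.** With no withdrawal effect, and normal, equally correlated scores, the highest of six readings minus one averages about 1.27 × sqrt(1 − rho) SD. That is 0.98, 0.80 and 0.57 SD at rho = 0.4, 0.6 and 0.8. There is no control arm to calibrate it.

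**Conclusion.** The point holds as a gap in the planned analysis. SAP 9.6, CT-13 and protocol 7.6.5 give separate observed-case summaries and no within-subject change after the last dose. Differences between rows therefore mix change with composition, and the Week 52/ET row can include scores taken after dosing stopped.

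The size is unknown. Under the assumptions shown, composition shifts the row difference by nothing with complete follow-up, by 0.05 SD at 90% response and by 0.15 to 0.24 SD at 70%. A paired change compares like with like and supports an interval, so it is the better estimate of withdrawal. It still carries selection and regression to the mean, and without a control arm a rise cannot be told apart from returning ADHD symptoms. The addition is worth making because it costs almost nothing and fixes the reference before the data are seen.

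**What to change.** In SAP 9.6 and CT-13, keep the planned rows and add one block:

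- Change in SMWQ total from Week 52/ET to each of Days 1, 2, 3, 5, 7 and 10, in subjects with both scores, with n, mean, SD and 95% CI.
- The Week 52/ET mean in those same subjects, and the number missing at each day. Set against the Week 52/ET mean in all subjects, the matched mean shows how selective the paired set is.
- The same overall and split by completers and early withdrawals. State what completer means for this split, because protocol 3.10 defines it by the Week 52/ET visit, which early terminators also attend.
- Reference scores taken on or before the day of the last dose for the main summary, with subjects whose reference score is later shown separately. A cut at one day after the last dose would overlap the Day 1 contact.

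Add a short note to 9.6. It should say that pairing removes the difference in who contributes to each row and improves precision by an amount that depends on an unknown correlation. It should also say that pairing does not remove selection or regression to the mean, and that a rise cannot be separated from returning ADHD symptoms. Do not report a mean largest increase.

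The cost is one extra block in one table, from data already collected.
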